### 12.4 Additional exploratory analysis

In addition to hypothesis testing, we will characterize the change in HPV viral load over the course of the trial using longitudinal data modeling. For each individual, we will have data on HPV viral load at weeks -2 (Screening visit), 9-10, and 15. A random effects model will be used to model the distribution of HPV viral load over time:

$$hpv_{it} = \beta_{0i} + \beta_1 t + \beta_2 t^2 + \varepsilon_{it}$$

where  $hpv_{it}$  is individual  $i$ 's HPV viral load at week  $t$ . Correlations between observations within an individual are accounted for by the random intercept (i.e. random effect) term. A quadratic model is used to account for non-linearity in the change of HPV viral load. From the fitted model, we can estimate the effect of the vaccine treatment on viral load. The plot below is based on simulated data and shows the type of result we hypothesize: a downward trend in HPV viral load that flattens as time increases. Based on the random effects model shown above, we can estimate the average response (denoted by the thick line) and better understand the association between the vaccine and response and specifically when changes in viral load tend to occur.

Lesion size will also be described using the random effects linear longitudinal model described above to look for time trends.

The secondary efficacy endpoints will be compared with analogous data obtained in a currently open cohort study, “Evaluation of Tissue and Peripheral Blood Immune Response in Women with HPV16+ Cervical Intraepithelial Lesions” (Johns Hopkins IRB# NA\_00037578). This observational cohort protocol has been open since 1999, and currently includes over 250 subjects. These subjects have the same eligibility criteria as the criteria for this trial, and are followed prospectively for the same timeframe, before undergoing standard therapeutic resection at week 15. To date, no CIN2/3 lesions have progressed to invasive disease in this timeframe, which is well within the standard of care. We will compare changes in HPV viral load and lesion size from baseline at Week 15, rates of histologic regression, and change in viral load over the 15 week window, in both cohorts.

We will correlate immune response with clinical response by looking at the association with disease regression. A logistic regression analysis will be performed with regression as the outcome and baseline and change between baseline and follow-up HPV viral load as predictors, where HPV viral load and the change have been transformed for normality. Using these two predictors, we can assess how change in viral load is associated with clinical response, adjusting for baseline level. Other predictors of interest will also be evaluated, including measures of E7-specific immune response. To explore the association between continuous outcomes of interest and time, the random effects model described above will be used.

The frequency and severity of all toxicities will be tabulated from CRFs and summarized for review in a descriptive fashion. The initial review of toxicity will be completed after the first treatment group has completed the intervention portion of the study (through week 5).

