**Study Population**

Women, 18 years and older, with biopsy-confirmed CIN2/3, and a visible lesion after biopsy.

**Inclusion/  
Exclusion  
Criteria**

Inclusion

- ≥ 18 years
- Capable of informed consent
- HPV-positive by DNA test
- Histologically confirmed CIN2, CIN3, or CIN2/3
- Body weight ≥ 50 kg
- Immune competent

[figure not shown]

	
Exclusion
 

• Pregnant and nursing women

• HIV seropositive

• Active autoimmune disease

• Taking immunosuppressive medication

• Evidence of concurrent adenocarcinoma in situ

• Concurrent malignancy except for nonmelanoma skin lesions

Investigational Treatment	Intra-vaginal administration of Artesunate suppositories, one to three multi-day dosing cycles; 50-200 mg, once a day for 5 days per treatment cycle; prior to scheduled LEEP or cone excisional procedure (standard of care for CIN2/3 patients)
Clinical Study Sites	Johns Hopkins Hospital Greater Baltimore Medical Center (Johns Hopkins Clinical Research Network Site)
Study Design*	Phase I open-label dose escalation study of intravaginal Artesunate, formulated in suppositories, in adult females with biopsy-confirmed CIN2/3. Thirty (30) subjects will undergo up to a total of three cycles of intravaginal Artesunate. The first cycle will be initiated on Day 0, the second at Week 2, and the third and final cycle at week 4. The lowest dose cohort that demonstrates most evidence of clinical efficacy as determined by clinical endpoints will be expanded. A schematic overview of the study design is provided on the next page, including study arms, sample size and schedule of interventions. An outline of scheduled visits and assessments is presented below.
Evaluation Criteria	Safety: Subjects will be monitored for local and systemic adverse events.  Efficacy: Histology, cytology, and HPV PCR at study week 15.
Number of Subjects	A total of 30 patients will be enrolled in this study
Estimated Patient Enrollment Period	12 months after the approvals of IND and JHH IRB

**Subject Participation Duration** 41 weeks from the first dosing

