### **9.1 Subject Inclusion Criteria**

- \* Patients with high-grade cervical intraepithelial lesions (CIN2/3) confirmed by colposcopy and biopsy.
- \* Patients who have measurable disease after diagnostic biopsy.
- \* Patients who weigh  $\geq 50$  kg
- \* Patients who are HPV-positive by DNA test
- \* Patients who are age 18 or older.
- \* Patients who are able to give informed consent.
- \* Patients who are immunocompetent.
- \* Patients who are not pregnant; committed to using adequate contraception through week 15 if of childbearing age. Condom use will be encouraged.
- \* Patients who have the ability to collaborate planned follow-up

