**Table 3: Outline of Evaluation Procedures**

	-3wks	Wk 0	Wk 2 	Wk 4 	Wk 6	Wk 15	Postop **	Wk 28	Wk 41
Informed consent	X								
Artesunate dosing		X	X	X					
Vital signs	X	X	X	X	X	X	X	X	X
Cervix check			X	X	X	X			
Medical history	X								
History of disease	X								
Demographic data	X								
Diary cards (give to pt)		X	X	X		X			
Diary cards (collect from pt)			X	X		X			
Adverse events		X	X	X	X	X	X	X	X
Inclusion/exclusion criteria	X								
Colposcopy	X				X	X		X	(X)*
Pap smear	X				X	X		X	X
HPV genotyping	X				X	X		X	X
Cervical swabs	X	X	X	X	X	X	X	X	X
LEEP/Cone**						(x)		(x)	
HLA testing ***	X								
PBL for banking****	X	(X)			X	X	X	X	X
Urine HCG	X	X	X	X		X			
Optional pheresis*****									

1. Treatment Group III

2. Treatment Group IV

\* Colposcopy only if clinically-required at wk 41

\*\* if residual disease is present (the procedure can happen any time after week 15, based on the physician's clinical judgment). The Postoperative visit will take place 4 +/- 1 weeks after the LEEP/Cone procedure.

\*\*\* HLA can be done at any time during the study, not an eligibility criterion

\*\*\*\* First blood draw can be done at either the screening visit or Wk 0, prior to dosing

\*\*\*\*\* pheresis is optional and can happen any time after week 15

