## 10.2 Intervals Between Visits

The intervals between screening and first administration may be  $3 \pm 2$  weeks, if necessary. A subject is considered enrolled when she receives the first Artesunate suppository at the scheduled Week 0 visit. After the first administration of Artesunate, the time window for each subject to complete 4 remaining daily doses of Artesunate suppositories may be between 4 days and 2 weeks (for example, to minimize potential wash-off of the treatment during a menstrual period). There will be a window of  $\pm 1$  week at weeks 2, 4, 6, 15, and post-operative visit, and  $\pm 2$  weeks at the week 28, and 41 visits.

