### 10.3 Description of Study Visits

All clinically relevant data collected during the study procedures must be recorded first in the patient file. These data will then be transcribed into the CRF. All visits will be outpatient visits.

At the initial screening visit, in addition to undergoing a standard of care colposcopic evaluation, we will obtain cervical brush specimens for HPV typing, and peripheral blood specimens to determine HLA phenotype, HIV status, and immunologic studies. Subjects with biopsy-confirmed CIN2/3 will be enrolled into treatment cohorts as depicted in Table 4 below.

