## **12.2 Secondary Endpoints**

Secondary endpoints include change in histology (CIN2/3 or no CIN2/3) at week 15 and changes in cervical HPV viral load. These endpoints are chosen because in other trials they have been shown to be quantifiable and reproducible. They do reflect the biology of HPV infection and cervical intraepithelial disease, and furthermore have been shown to be modulated in response to intervention in other trials.[67] The histological outcome will be determined by comparing the initial diagnostic biopsy used for protocol entry with the exit cone resection. HPV viral load will be ascertained from longitudinally obtained cervical cell samples, using quantitative PCR.[68] This data will be used to estimate the regression rate within the fifteen-week window in the exploratory analysis.

Secondary endpoints will also include change in lesion size by colposcopy, and characterization of peripheral and local tissue response to the suppository. These measures will be correlated with clinical response, and with preclinical experimental data in the exploratory analysis. In every case possible, changes in lesion size by colposcopy will be ascertained by analyzing serially obtained digital colposcopic images. Measures of immune response will be ascertained on serially obtained peripheral blood specimens, and on flash frozen tissue from the therapeutic resection specimens.

To test that HPV viral load is different during and after treatment as compared to before treatment, paired t-tests and signed rank tests will be used. Log transformation (or other appropriate transform) will be performed to symmetrize the distributions and achieve normality. For each of these variables, a paired t-test will be performed. Due to the small sample size and potential non-normality of the data, the non-parametric signed rank test will also be used. The paired t-test tests whether or not the mean HPV viral loads at baseline and follow-up are

equivalent, whereas the Wilcoxon matched-pairs signed-ranks test tests whether the distributions of HPV viral loads is the same at baseline and follow-up.

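### The only pre-treatment viral load named in section 12.4 is the screening sample, 1 to 5 weeks before any drug; sections 12.1 and 12.2 leave baseline undated, although a week-0 swab is scheduled

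*Combined protocol and SAP*

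**What the plan says.** **Viral-load times.** Section 12.4 states: "For each individual, we will have data on HPV viral load at weeks -2 (Screening visit), 9-10, and 15". Its random-effects model has a random intercept, a linear and a quadratic term in week, and nothing else. The section says that the effect of treatment on viral load can be estimated from this fit.

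**Timing of screening.** Section 10.2: "The intervals between screening and first administration may be" 3 ± 2 weeks. It also fixes the start of treatment: "A subject is considered enrolled when she receives the first Artesunate suppository at the scheduled Week 0 visit".

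**Selection at screening.** Section 9.1 admits "Patients who are HPV-positive by DNA test". Section 10.3 says: "At the initial screening visit, in addition to undergoing a standard of care colposcopic evaluation, we will obtain cervical brush specimens for HPV typing". Table 3 marks genotyping and the eligibility check at screening and neither at week 0.

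**Tests and decision rule.** Section 12.2 introduces paired t-tests and signed rank tests thus: "To test that HPV viral load is different during and after treatment as compared to before treatment". It does not say which sample represents the period before treatment. Section 12.1 chooses the expansion dose partly on significant within-woman falls in viral load between baseline and week 15, again without dating baseline.

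**Week 0 elsewhere.** Section 12.3 uses week 0 as the starting point for lesion size and T-cell response. The Table 3 row "Cervical swabs" is marked at every visit, including week 0.

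**The concern.** A baseline taken before the first dose but some weeks away from it brings two things into the before/after difference that the drug cannot have caused. One is any change between screening and first dose. The other is regression to the mean: a woman admitted on a positive result tends to have a somewhat lower value on repeat. Both push towards an apparent decrease, and the first varies between women with the length of their screening interval.

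The plan itself expects untreated change. Section 5.0 cites spontaneous regression of about 20-25% of HPV16-associated lesions in this timeframe, and more for other genotypes. At stake are the interpretation of a secondary endpoint and, if the undated baseline in section 12.1 is the screening value, one of the two criteria for choosing the expansion dose. That rule is a within-woman comparison with no control.

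**Working it through.** The plan gives no effect size, standard deviation or power for viral load, so there is no figure of its own to reproduce.

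**1. Lag from screening to first dose.** From section 10.2: 3 − 2 = 1 week to 3 + 2 = 5 weeks. Section 12.4 places screening at week −2 and Table 3 at −3.

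**2. Untreated share of the interval.** Share = s / (s + 15), with s the lag in weeks and first dose at week 0:

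| Lag s (weeks) | Untreated share | Share after first dose |
|---|---|---|
| 1 | 1/16 = 6.3% | 15/16 = 93.8% |
| 2 | 2/17 = 11.8% | 15/17 = 88.2% |
| 3 | 3/18 = 16.7% | 15/18 = 83.3% |
| 5 | 5/20 = 25.0% | 15/20 = 75.0% |

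With the ±1 week window at week 15, the extremes are 1/17 = 5.9% and 5/19 = 26.3%. If natural decline is steady on the log scale (an assumption), the middle column is also the share of spontaneous change that falls before any drug.

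**3. What the model does with it.** The three coefficients describe one smooth curve through screening, weeks 9-10 and week 15. Nothing separates the segment before dosing from the segment after it, so change between screening and first dose belongs to the curve that is read as the treatment effect.

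**4. Possible effect on a paired test.** This is a simulation with no drug effect: n = 9 (one 200 mg cohort), paired t-test at two-sided 0.10, counting only significant decreases, so the nominal rate is 5%. All other inputs are assumed: mean 5 log10; between- and within-woman SDs of 1.5 and 0.5, 1.5 and 1.0, or 1.0 and 1.0; entry only if the screening value reaches 2, 3 or 4 log10; lag 3 weeks.

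| Assumed natural decline | Screening baseline | Week-0 baseline |
|---|---|---|
| None | 5.4% to 14.0% | about 5% |
| 0.03 log10 per week | 30% to 77% | 22% to 54% |

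With no decline, regression to the mean alone is 0.01 to 0.29 log10, smallest when the entry threshold lies far below the mean. With decline, the true untreated change is 0.03 × 18 = 0.54 log10 from screening and 0.03 × 15 = 0.45 from week 0. The difference of 0.09 is 16.7% of 0.54, as in step 2.

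**5. Consistency of the listed times.** Screening is week −2 in section 12.4 and −3 in Table 3. Weeks 9-10 match no visit in Table 3, whose interval visit is week 6.

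**The case against.** - **The week list belongs to an exploratory model.** This stands. A reader might infer that the paired tests and the expansion rule certainly use screening. The documents do not say so: sections 12.1 and 12.2 give no date, and screening is only suggested by section 12.4 and by section 10.4, which describes viral-load specimens with the colposcopy visits. The reach to dose selection is conditional.
- **The week-0 swab may already be meant for viral load.** Section 7.2 says serial swabs will be used to quantify it, whereas section 10.4 ties specimens to colposcopy visits and banks swabs of secretions. It is therefore not established that the week-0 swab goes unused, nor that it is already due for PCR.
- **Most natural decline comes after week 0.** This also stands: 75-94% under steady decline. The lack of a concurrent control is the larger problem, and moving baseline does not cure it.
- **The untreated cohort in section 12.4 may offset the bias.** It may in that comparison, if both cohorts' baselines are taken at the same point relative to entry, which is not stated. It does not protect the within-woman rule in section 12.1.
- **Safety is primary and the analysis mainly descriptive.** True. The expansion rule also requires lesion clearance and falls back on the overall safety and efficacy profile. This limits the consequence but does not justify leaving baseline undated.

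**Conclusion.** The point holds in a limited form. Followed as written, section 12.4 counts change before the first dose as treatment effect, and sections 12.1 and 12.2 leave open whether the paired tests and the expansion rule do the same. If screening is the baseline, about 6-25% of the interval to week 15 is untreated for lags of 1 to 5 weeks, and selection on a positive test can add regression to the mean.

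A reader might infer that the bias is large. The documents do not support that. They give no viral-load decline rate, variance or assay cut-off; the 20-25% in section 5.0 is histologic regression; and the simulated rates rest on assumed inputs. The bias may be small. A week-0 baseline removes the pre-dose change and the artefact of selection at screening, not spontaneous decline during weeks 0-15. The change is still worth making, because the swab is already scheduled and section 12.3 already uses week 0 for other endpoints.

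**What to change.** 1. **Table 3.** State that the week-0 swab is taken before the first suppository and is assayed by quantitative PCR. Section 10.3 has the first suppository inserted in clinic, while section 11.2 has all daily doses given at home. These passages must be reconciled so that pre-dose has a clear meaning.
2. **Sections 12.1 and 12.2.** Define baseline viral load for the paired tests and the expansion rule as the week-0 pre-dose value, with screening used only if week 0 is missing.
3. **Section 12.4.** Use actual time from first dose and align the listed weeks with Table 3. Either start the model at week 0, or keep screening and add a pre/post-dose term (a knot at t = 0). Keeping screening in a single quadratic does not isolate the pre-dose slope, and the knot relies on the week-0 value being assayed.
4. **External cohort.** Use the same entry-relative sample as baseline in both cohorts, for that comparison only.

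The cost is one more PCR per woman, one table footnote, some analysis wording and a separately defined baseline for the cohort comparison. No visit or procedure is added.

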#### **5.0 RATIONALE FOR CLINICAL TRIAL DESIGN**

This trial is a prospective, open, dose-escalation study of topical Artesunate, formulated as a suppository, administered intravaginally, prior to standard therapeutic resection of the squamocolumnar junction at study week 15. An initial dose cohort of 3 subjects will receive intravaginal Artesunate for one 5-day treatment cycle. Based on clinical experience with Artesunate, we expect that absorption in the cervical mucosa, which is stratified squamous epithelium, will be less than what is observed with rectal administration, which is a single layer of glandular epithelium. Because cervical stroma is much less vascularized than colorectal stroma, we also expect significantly lower systemic levels of Artesunate in subjects receiving intravaginal dosing. The goal of topical administration is to achieve local, mucosal distribution of study drug, as opposed to systemic levels.

If we do not observe untoward side effects, including mucosal excoriation, in the first dose cohort, we will proceed with dose-escalation. The subsequent cohort will undergo two cycles of treatment, spaced at 2-week intervals. The final cohort will undergo a total of three cycles of treatment, spaced at 2-week intervals. All subjects will undergo an interval colposcopic exam at study week 6. At week 15, if there is still a colposcopically detectable lesion, subjects will undergo standard therapeutic resection. If no lesion is obvious, a biopsy will be taken at the site of the original lesion. The cohort receiving the fewest cycles of Artesunate, and showing therapeutic effect will be expanded (see Section 12 for details). At each vaginal exam, cervical swabs will be obtained and cryopreserved. Peripheral blood will be obtained by venipuncture at baseline, and at study weeks 5, 15, and 28, 41, and the postop visit, and will be cryopreserved for assessment of biomarkers.

This clinical cohort, healthy subjects with colposcopically-directed, biopsy-confirmed CIN2/3, was selected for safety reasons. The study protocol window (15 weeks), is within the standard of care. In pregnant women who have a cervical HSIL, the standard of care is to follow colposcopically until postpartum [7]. We and others have reported that the probability that CIN2/3 will progress in this timeframe is essentially zero [63]. In fact,

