### **7.2 Secondary Outcome Measures**

Indicators of drug efficacy (see below) will be drawn from any evidence demonstrating a significant difference (by simple chi-square analysis;  $p < 0.1$ ) between treated subjects and the baseline data in the Johns Hopkins Colposcopy database

- Extent of lesion clearance (by lesion number, size, and/or area of coverage)
- Presence/absence of HPV DNA
- Regression of CIN stage by histopathology (comparison of initial biopsy to LEEP/cone excision-procured tissue).

Histologic regression will be judged as none (persistent CIN2/3 in week 15 resection specimen) or total (no CIN2/3 in resection specimen).

Virologic HPV viral load. Longitudinally obtained cervical swabs will be used to quantitate HPV viral load as a continuous variable.

Tissue sections from the diagnostic biopsy obtained as part of the screening process, and from the resection specimen obtained post-treatment will be assessed for expression of CD8 (effector T cells), CD71 (transferrin receptor), and cleaved caspase 3 (apoptotic cell death).

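### The Section 12.4 quadratic is fitted to three viral-load visits, none during dosing, so it cannot show when between screening and week 9-10 the change occurs

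*Combined protocol and SAP*

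**What the plan says.** Section 12.4 lists the data: "For each individual, we will have data on HPV viral load at weeks -2 (Screening visit), 9-10, and 15". The mean model has an intercept, a linear and a quadratic term in week, common to all women apart from the intercept. On the form it says "A quadratic model is used to account for non-linearity in the change of HPV viral load", and on the random part "Correlations between observations within an individual are accounted for by the random intercept". The expected result is "a downward trend in HPV viral load that flattens as time increases". One stated use of the fitted curve is to understand "specifically when changes in viral load tend to occur".

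On dosing, the Synopsis says "The first cycle will be initiated on Day 0, the second at Week 2, and the third and final cycle at week 4". Section 10.2 lets a woman take up to two weeks to finish a cycle and gives the week 2, 4 and 6 visits a window of one week either way, so dosing ends by about week 7 at the latest.

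Other parts of the plan do not match the three-visit list:
- Table 3 has no week 9-10 visit, places screening at week -3, and marks cervical swabs at screening and weeks 0, 2, 4, 6 and 15, among others.
- Section 5.0: "At each vaginal exam, cervical swabs will be obtained and cryopreserved".
- Section 7.2: "Longitudinally obtained cervical swabs will be used to quantitate HPV viral load as a continuous variable".
- Section 12.2 plans to test viral load during treatment as well as after it. The 12.4 visits cannot supply an on-treatment value.
- Section 10.4 describes viral-load specimens under the colposcopy visits (screening, weeks 6, 15 and 28).

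**The concern.** A three-parameter mean on three time points has no degree of freedom left to test its own shape. No listed visit lies between screening and week 9-10, so the whole dosing period is unobserved. A reader of the fitted plot will still take the smooth line through weeks 0 to 9 as evidence about when the drug acts. At stake is a wrong statement on onset: part of a post-dose fall may be shown as already under way before any drug was given. The issue is the functional form and the visit list, not the random intercept.

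**Working it through.** The plan gives no numerical result for this model, so there is no figure to reproduce.

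**Inputs.** Visit times -2, 9.5 (midpoint of 9-10) and 15, from Section 12.4. First dose at week 0, from the Synopsis. Assumed, because the documents give no profile: no change before week 0, total fall of 1 unit on the transformed scale from screening to week 15, and a fraction r of that fall present at week 9.5.

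**Step 1: is shape estimated?** The design matrix (1, t, t²) at three distinct times has rank 3. At nominal times the fitted mean equals the three visit means. A step drop at week -1, 0.1, 2, 5 or 8 gives the same three means (0, -1, -1) and hence the same curve, so timing inside that interval is not identified.

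**Step 2: fitted value at week 0.** Interpolating with f(-2) = 0:
- weight on week 9.5: (2 × -15)/(11.5 × -5.5) = 30/63.25 = 0.4743
- weight on week 15: (2 × -9.5)/(17 × 5.5) = -19/93.5 = -0.2032
- share of the fall drawn before the first dose = 0.4743r - 0.2032

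| Case | r | Share before week 0 |
|---|---|---|
| Effect complete by week 9.5 | 1 | 27.1% |
| 80% present at week 9.5 | 0.80 | 17.6% |
| Visit means on a straight line | 11.5/17 = 0.676 | 2/17 = 11.8% |
| True straight decline, weeks 0 to 15 | 9.5/15 = 0.633 | 9.7% |
| Half present at week 9.5 | 0.50 | 3% |
| 30% present at week 9.5 | 0.30 | -6% |

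The visit means show a decline that flattens only when r exceeds 0.676, hence the floor of about 12% under the hypothesised shape.

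**Step 3: sensitivity.**
- For r = 1, a middle visit at week 9 or 10 gives 27.8% or 26.5%. Screening at week -1, -3 or -5 (Section 10.2 allows 3 ± 2 weeks before dosing) gives 15%, 37% or 51%.
- Week 6 as the middle visit, with the effect complete by then, gives 34% (screening -2) or 44% (screening -3).
- Exponential onset from week 0 with half-life 1, 2, 3, 4, 6 or 8 weeks gives 27%, 26%, 23%, 21%, 18% or 16%.
- A random-intercept simulation with visit windows (9 women; assumed SDs 1 between and 0.5 within; effect 2 log units; half-life 1 to 4 weeks) gives 18% to 25%. The windows make the fit slightly less than exact but do not remove the artefact.

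**Step 4: do more visits alone cure it?** No. A single quadratic fitted to screening and weeks 0, 2, 4, 6 and 15 still draws 20% to 47% of the fitted change before week 0 (half-life 0.5 to 4 weeks, screening at -2 or -3).

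**Step 5: does one knot at first dose cure it?** No. Take an immediate, complete effect: 0 at screening and week 0, then -1 at weeks 2, 4, 6 and 15. The pre-dose slope fits the screening point exactly, so the post-dose line is least squares on weeks 0, 2, 4, 6 and 15. Mean t = 5.4 and mean y = -0.8; Sxy = (-5.4)(0.8) + (5.4)(-0.2) = -5.4; Sxx = 135.2; slope = -5.4/135.2 = -0.040. The fitted value at week 0 is -0.8 + 0.040 × 5.4 = -0.58, so 58% of the true fall is placed before dosing. More gradual onsets give about 13% to 56%. Visit as a factor, with a week-0 value, gives 0% in expectation.

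**The case against.** The best defence is that the artefact depends on the true profile, which the documents do not give. A reader might infer that the model puts a large part of any drug effect before the first dose. The table above does not support that: a slow or late effect gives under 10% or a negative share. Some early decline could also be real, since Section 5.0 expects spontaneous regression of 20-25% of HPV16 lesions in this timeframe.

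A reader might also infer that the parabola must show a false rebound. Section 12.4 hypothesises flattening and does not say that the load then stays flat. With r = 0.80 the fitted minimum is near week 21.6, after the last modelled visit. With r = 1 it is at week 12.25, where the curve is at -14.25²/195.5 = -1.04, an overshoot of about 4%. A rebound of about 23% appears only with visits at weeks 0, 6 and 15 and an effect complete by week 6 and then flat. Exponential falls with time constants of 3 and 5 weeks reduce it to 12% and 3%.

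Nor is it right that the model says nothing on timing: the three means do separate change by week 9-10 from later change. The three-visit list may simply be unreconciled with Table 3. Finally, the analysis is labelled exploratory, and the choice of expansion dose in Section 12.1 uses week-15 change and lesion clearance, with the paired tests of Section 12.2.

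All of this stands and limits the size of the point. What remains is that shape and timing before week 9-10 are assumed while the text claims to learn them, and that the visit list contradicts the schedule.

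**Conclusion.** The point holds in a limited form. As written, Section 12.4 cannot show when within weeks -2 to 9-10 viral load changes, and this needs no assumption beyond the listed visits and the quadratic mean. The pre-dose share is conditional: more than about 12% if the decline flattens and nothing changes before week 0, and about 27% if the effect is also complete by week 9-10, both with screening at week -2. It does not extend to slow or late effects, and a material false rebound is not a general consequence. The conflict with Table 3 holds independently of these figures. No primary result, paired test in Section 12.2 or dose selection in Section 12.1 depends on the curve, so this is a minor correction.

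**What to change.** In Section 12.4:
- Reconcile the viral-load visit list with Table 3.
- Replace the linear and quadratic terms in week by visit as a categorical factor and keep the random intercept. Use the swabs through week 15 that suit quantitative PCR: at least screening or week 0, week 6 and week 15. A statement about change before dosing needs both screening and week 0.
- Report week 2 and week 4 means within cohorts III-IV only, because Table 3 ties those visits to these cohorts and a pooled mean would mix visit with regimen.
- Do not use a single knot at first dose with a straight line afterwards; it reproduces the artefact.
- If only three visits are assayed, report the three visit means with confidence intervals and delete the claim that the model shows when changes occur.

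The cost is a small wording change, plus PCR on banked swabs if the extra visits are used. The sponsor should first confirm that the week 0, 2 and 4 swabs are suitable, since Section 10.4 mentions viral-load specimens only with colposcopy. Week 2 and week 4 estimates will be less precise because they rest on fewer women.
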